## DOCUMENT REVISION HISTORY PAGE

Document Number:	Rev:	Page:		
90D0153	A	2 of 17		
Title: Heart Sounds Measurement Using the Wearable Cardioverter Defibrillator (HS-WCD): Study Protocol				
Revision History Of Document				
Rev	CO Number	Description of Change	Author	Effective Date
FI	NA	First issue	RP	1/15/14
A	0182	
Exclusion criteria were expanded to include subjects with pacemakers; implanted defibrillators, and cardiac resynchronization therapy devices; and subjects with a previous history or current diagnosis of atrial fibrillation.
 
Added a note that subject's blood pressure and heart rate will be measured once the subject is eligible to participate in the study.
	RP	2/11/16

## PROTOCOL SUMMARY

### Objectives

To conduct a prospective, validation study to evaluate the data accuracy of heart sounds recorded by the LifeVest® Wearable Cardioverter Defibrillator (WCD). To show equivalence, these data will be compared with the heart sounds data recorded by the FDA-cleared AUDICOR® AM device.

### Study Size

The study will enroll a minimum of 27 and a maximum of 35 subjects.

### Study Population

Participants will be adult patients (age  $\geq$  18 years) with at least seven patients over the age of 40 years. In addition, at least five patients with a history of heart failure will be included.

### Intervention

First, participants will wear the AUDICOR® AM device for 15 minutes while sitting quietly. Then, the AUDICOR device will be removed and the participants will wear the WCD for 15 minutes while sitting quietly. Next, while wearing the WCD, participants will perform various activities of daily living, including at least 6 hours of overnight wear. Finally, the WCD will be removed and the participants will wear the AUDICOR® AM again for 15 minutes while sitting quietly.

### Study Design

This is a single center, prospective, observational study. This is a non-significant risk device study as all biological study parameters will be measured noninvasively with the WCD defibrillation capability disabled. In addition, the study device will not be used as a replacement for regularly prescribed therapies or diagnostics.

## 1. INTRODUCTION

[figure not shown]
Heart sounds represent vibrations of the cardiohemic system (cardiac cavities, valves, and blood) due to acceleration and deceleration of blood, as result of pressure gradients . These sounds are a direct expression of mechanical activity of the cardiovascular system and can be used to identify significant events in the cardiac cycle as well as detect irregular heart activity. For example, the presence of the third heart sound (S3) is recognized to be a clinical sign of left ventricle dysfunction and a predictor for adverse outcomes in patients with heart failure .

Acoustic cardiography is a diagnostic technique that consists of recording and algorithmically interpreting the heart sounds with concurrently recorded electrocardiogram (ECG) data . This technique allows for identifying normal and abnormal heart sounds, and quantifying the timing of these heart sounds with respect to the cardiac electrical activity. These data can then be used to identify patients with cardiac dysfunction such as those with systolic heart failure .

The ZOLL LifeVest® Wearable Cardioverter Defibrillator (WCD) is an FDA-approved device that noninvasively monitors ECG signals during activities of daily living. If a life-threatening ventricular tachyarrhythmia is detected, the device automatically provides external defibrillations in an attempt to restore a normal heart rhythm. Given the diagnostic utility of acoustic cardiography, ZOLL has modified its WCD system to incorporate a sensor to record heart sounds while simultaneously recording the ECG signals. To evaluate the data accuracy of the heart sounds recorded by the device, the WCD heart sounds data collected by a modified unit will be compared with the data recorded by the AUDICOR® AM system (Inovise Medical, Inc, Portland, OR), which is a FDA cleared, non-invasive, ambulatory, acoustic cardiography recorder.

## 2. SYSTEM DESCRIPTION

### 2.1 LifeVest® WCD system

[figure not shown]

**Figure 1:** Components of the WCD system with the heart sounds sensor (see text for details).

The WCD is composed of four dry, non-adhesive monitoring electrodes and three defibrillation electrodes incorporated into a lightweight vest (garment), that are connected to a defibrillation unit (monitor) carried in a holster, which can be supported by over-the-shoulder strap or worn

on the hip (Fig. 1). The monitoring electrodes are positioned circumferentially around the chest to provide two surface ECG leads. One defibrillation electrode is placed in an apical position while the remaining two defibrillation electrodes are placed posteriorly. The apical defibrillation electrode is modified to incorporate a heart sounds sensor, such that the sensor sits left of the xiphoid process over the 5th intercostal space (Fig. 1). For the purposes of the study the defibrillation capability of the WCD will be disabled.

## 2.2 AUDICOR® AM system

**Figure 2:** Components of the AUDICOR AM device (see text for details). RA-right arm; LA-left Arm; LL-left leg; V3 and V4 are precordial ECG positions.

The AUDICOR® AM device consists of three adhesive ECG electrodes arranged to form two bipolar limb leads, lead I (RA-LA) and lead II (RA-LL) (Fig. 2). In addition, there are two dual-purpose adhesive sensors in the V3 and V4 precordial positions that simultaneously acquire ECG and heart sounds data from each of these locations. The ECG and heart sound sensors are wired to a lightweight recording device that is placed on the right upper abdomen below the chest wall. The device performs automated acoustic measurements incorporating digital signal processing algorithms to detect and characterize the intensity and timing of heart sounds.

## 3. OBJECTIVES

The objectives of the study are to:

- 3.1 Compare the heart sound measurements recorded by the AUDICOR® AM device versus those recorded by the WCD while subjects are sitting quietly.
- 3.2 Observe the variation of heart sound measurements recorded by the WCD across subjects with specific physical maneuvers, time, and repositioning (due to removal and reapplication) of the WCD.
- 3.3 Observe measurements of the sleep-disordered breathing index recorded by the WCD.

## 4. SUBJECT SELECTION CRITERIA

The following criteria will be used to include subjects in the study:

---

- 4.1 Healthy male and female volunteers who are able to fit in the WCD garment (26 to 56 inches measured circumferentially at the level of the xiphoid process).
- 4.2 Included in this group are at least five healthy subjects with a self-reported history of heart failure.
- 4.3 The subject must be 18 years of age or older on the day of screening, with at least 7 subjects 40 years of age or older on the day of screening.

The following criteria will be used to exclude subjects from the study:

- 4.4 Mental, visual, physical, literacy, and auditory limitations that prevent interaction with the WCD equipment.
- 4.5 Any acute medical conditions that prevent the following maneuvers: lying on back, lying on the right and left side, standing, sitting, and/ or leaning forward when sitting.
- 4.6 Any self-reported shortness of breath, fatigue, swelling of feet, ankles, or legs, and/or chest pain.
- 4.7 Currently has a pacemaker, an implanted cardioverter defibrillator (ICD), or a cardiac resynchronization therapy (CRT) device.
- 4.8 A previous history or current diagnosis of atrial fibrillation.
- 4.9 Employees or family members of Inovise and ZOLL.
- 4.10 Unable or unwilling to provide written informed consent.

## **5. PROCEDURE**

At the beginning of the study a ZOLL representative will train the site study staff in AUDICOR AM and WCD device use. All testing will be performed on the site's premises. Before testing, ambient noise in the room should be minimized and if possible, the subject should be positioned away from sources of possible electrical interference.

### **5.1 Eligibility**

Potential subjects will be screened to determine whether they meet the inclusion and exclusion criteria.

[figure not shown]
### **5.2 Consent**

Informed consent will be obtained.

### **5.3 Enrollment**

Once enrolled, each subject will be assigned a sequential identification number. Subject's clinical history will be assessed and will include measurement of blood pressure and heart rate.

#### 5.4 AUDICOR® AM device setup and first use

**Figure 3:** Placement position of the AUDICOR AM sensors. RA, LA, and LL represent the ECG sensors and S3 and S4 represent the dual heart sounds and ECG sensor (see text for details).

[figure not shown]
Setup of the AUDICOR device will follow the procedures described in AUDICOR® AM quick reference guide and will include:

- Inserting a blank 2 GB data storage card and a fully charged battery in each of the recording devices.
- Ensuring the skin is clean and dry where the electrodes are to be placed. Remove any debris, ointment, etc. with water and mild soap. Wipe off any excess moisture with a dry cloth.
- Shave excess hair before applying the electrodes.
- Applying the adhesive ECG electrodes: RA is applied below the right clavicle; LA is applied below the left clavicle; and LL is applied on the left upper abdomen below the chest wall (Fig. 3).
- Applying the dual heart sounds and ECG adhesive sensors: S3 is applied approximately in the V3 lead position, below the 4th intercostal space right of the left midclavicular line (Fig. 3). S4 is applied approximately in the V4 lead position, along the mid-clavicular line in the 5th intercostal space.
- Marking the sensor placements in the case report forms.
- Connecting the electrodes/sensors to the recording device via the patient cables, matching the labeling on the cable to the electrodes as shown in Figure 3.
- Placing the AUDICOR recording device in the holsters and applying the assembly vertically on the right upper abdomen below the chest wall.
- Securing the lead wires with tape to the chest with proper strain relief to prevent cable movement.
- Having the subjects sit in a chair comfortably, with their back straight. Instruct them to be relaxed, quiet and still as possible while sitting.
- Configuring the device to preview the data quality and then initiating the recording by:
  - Launching the Cardio-Pulmonary Holter (CiPH) program from the sponsor provided laptop
  - Launching the patient setup from the CiPH interface

- Entering the appropriate sensor identification information in the patient setup
- Previewing the waveform from 3 ECG channels, labeled as I, II and V4RA, and 2 heart sounds sensor channels, labeled as SV3 and SV4
- Tapping near the heart sounds sensors, S3 and S4 and verifying that artifact from the tapping is observed on the preview
- If unable to see artifact, ensuring the cables are connected to the sensors and AUDICOR device, and if necessary, replacing the electrodes
- Entering patient number, and clicking start recording on the CiPH program to initiate the session.

Once the recording session is initiated, subjects will wear the AUDICOR device for 15 minutes while sitting quietly. During this time subjects are expected to be relaxed, quiet and as still as possible. After 15 minutes, the recording will be terminated by pressing the ON/Stdby buttons on the recording devices until the LED stops flashing. Then, the AUDICOR device will be disconnected and all electrodes/sensors will be removed from the subject's body. Finally, the battery of the recorder will be removed to access the data storage card. The data stored in the card will be transferred to a sponsor provided computer (for details, see AUDICOR® AM quick reference guide). Data from each subject will be stored under their previously assigned unique identification number.

## 5.5 WCD device setup and use

**Figure 4:** WCD vest placement on the subject with location of the WCD heart sounds sensor.

Application of the WCD will follow the procedures described in the LifeVest® Clinician Manual and will include:

- Programming the monitor and entering subject's identification number.
- Measuring the subject's chest size with the measuring tape centered at the xiphoid.
- Selecting the appropriate vest/garment size based on the chest size measurement.
- Assembling the garment with the monitoring and defibrillation electrodes, with the electrode belt disconnected from the monitor.

- Placing the assembled garment on the subject such that all clothing, including underwear, is worn over the device and not under it.
- Marking the location of the WCD heart sounds sensor in the case report form.
- Inserting a fully charged battery, connecting the electrode belt to the monitor, and starting the baseline process.
- Ensuring that the baseline process is successfully completed.
- Setting up the charger to allow for downloading of WCD monitoring data.

Following 5 minutes of inactivity for ECG stabilization, subjects will sit quietly for 15 minutes. The beginning of sitting will be marked by tapping the WCD front therapy electrode twice and noting the time. During testing, subjects are expected to sit in a chair comfortably, with their back straight. Instruct them to be relaxed, quiet and still as possible while sitting. At the end of 15 minutes, the front therapy electrode will be tapped twice and the time noted.

Subjects will then perform the activities of daily living (ADL) maneuvers listed below for 10 minutes each.

- 5.5.1 Standing
- 5.5.2 Lying on the back
- 5.5.3 Lying on the left side
- 5.5.4 Lying on the right side
- 5.5.5 Sitting and leaning forward

After settling into the new position, the front therapy electrode will be tapped twice by the test administrator, the time after tapping will be noted as the start time, a manual recording will be performed by holding the response buttons for 3-seconds, and at the end of 10 minutes the front therapy electrode will be tapped and the time will be noted as the stop time. After all ADL maneuvers are complete, the study coordinator will remove the WCD device by disconnecting the electrode belt, unplugging the battery from the monitor, and removing the garment off the subject. After five minutes, the garment will be reapplied and then electrode belt and battery will be reconnected to the monitor. The subject will wear the device for 10 minutes while sitting quietly. The removal and reapplication times will be noted.

Following the removal and reapplication section, the subject will continue to wear the WCD until the total use of the device is 12 to 16 hours, with at least 6 hours of overnight wear. During the overnight wear the subject will be expected to sleep at the testing site. In addition, subjects will fill a diary (see Appendix A) to note their non-testing WCD activities before and after sleeping; any non-testing activity that causes the device to alarm; and any activity while sleeping that causes the WCD to alarm.

After the overnight wear, removal and reapplication of the WCD device will be repeated, following the procedure as described previously, and the subject will wear the device for 10 minutes while sitting quietly. At the end of the testing, recording from the WCD device will be terminated by removing the battery and the garment will be removed from the subject. Data from the WCD device will be downloaded to the ZOLL servers. In addition, at the end

---

of testing each subject, the WCD monitor will be cleaned, packed appropriately, and returned to ZOLL.

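### The order of the five posture maneuvers is not counterbalanced, so within that block posture differences can be separated from order or elapsed time only by modelling the plan does not include

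*Combined protocol and SAP*

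**What the plan says.** Objective 3.2 (Section 3) is to "Observe the variation of heart sound measurements recorded by the WCD across subjects with specific physical maneuvers, time, and repositioning" of the WCD. Maneuver, time and repositioning are named side by side as sources of variation.

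Section 5.5 sets out the WCD session:

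- Before the postures: "Following 5 minutes of inactivity for ECG stabilization, subjects will sit quietly for 15 minutes".
- The posture block: "Subjects will then perform the activities of daily living (ADL) maneuvers listed below for 10 minutes each". The list runs from "5.5.1 Standing" through lying on the back, the left side and the right side to "5.5.5 Sitting and leaning forward". Each posture appears once. Timing of each one starts only after the subject has settled into it.
- After the block, the garment is taken off for five minutes and put back on: "The subject will wear the device for 10 minutes while sitting quietly".
- Next day: "After the overnight wear, removal and reapplication of the WCD device will be repeated", with another 10 minutes of quiet sitting. Total wear is 12 to 16 hours.

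Section 6 has the coordinator record the start and end time of each maneuver, and says the WCD stores complete heart sound recordings. Section 7 plans descriptive and qualitative comparisons across maneuvers, around reapplication and across time, and states that none of them carries an endpoint. Section 8 bases equivalence on quiet-sitting EMAT alone.

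Nothing in Sections 5.5, 6 or 7 says whether the listed order is to be followed, or whether it should vary between subjects.

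**The concern.** A numbered list in a procedure section will normally be carried out as numbered. Standing then always comes first and leaning forward always comes last, 40 minutes later or more. Anything that changes over the session, such as electrode contact, garment position or resting heart rate, moves in step with posture in every subject. Each posture also always follows the same predecessor, so any carry-over is attached to posture as well.

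A table of EMAT or LVST by posture would then show posture and place in the sequence mixed together. A reader of that table could not tell whether lying on the right side differs from standing because of the posture or because it came half an hour later. That is the comparison Objective 3.2 asks for. More subjects would not help, since each would add the same pattern.

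**Working it through.** The plan states no figure on this point, so there is none to reproduce. The check is whether posture and time effects can both be estimated, judged by the rank of the design matrix: if the rank is below the number of parameters, some effects cannot be told apart.

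**Inputs (Section 5.5).** 5 min stabilisation, 15 min sitting, five postures of 10 min, 5 min off, 10 min sitting, and a last 10 min of sitting. Assumptions: listed order followed by all, no gaps between postures, and the last sitting window placed at the end of 12 or 16 h.

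**Window midpoints in minutes.** Sitting 12.5; standing 25; back 35; left 45; right 55; leaning forward 65; sitting after the first reapplication 80; last sitting 715 (12 h) or 955 (16 h). First to last posture: 65 − 25 = 40 min.

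**Results if the listed order is used for all** (the same for 12 h and 16 h):

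| Data and model | Parameters | Rank | Separable? |
|---|---|---|---|
| Five posture means + free period effects | 9 | 5 | No |
| Five posture means + linear time | 6 | 5 | No |
| Adding the initial sitting window | 7 | 6 | No |
| Adding both later sitting windows, one common reapplication effect | 8 | 8 | Yes |
| Same, a separate effect for each reapplication | 9 | 8 | No |
| Minute-level data within the five windows + linear time | 6 | 6 | Yes |

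**Results with a five-row Latin square of orders.** Posture + free period effects: 9 parameters, rank 9. Separable without assuming any shape for the time trend, apart from carry-over.

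**What the two routes under a fixed order assume.**

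- *Later sitting windows.* Three sitting windows must supply the sitting level, the slope and the reapplication effect. That works only if both reapplications have the same effect. The slope then rests on the last two sitting windows, 715 − 80 = 635 min or 955 − 80 = 875 min apart, and is applied to a 50-minute block. Drift must be linear across a night's sleep.
- *Within-window data.* The slope comes from change inside each 10-minute window and must be common to all postures. Remaining posture-specific settling would be read as drift.

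**What rotation does.** With equal rows, each posture's mean position is (1+2+3+4+5)/5 = 3, so a linear trend cancels. With 27 subjects the rows hold 6, 6, 5, 5 and 5. In a cyclic square whose first two rows take the extra subjects, the mean positions range from 78/27 = 2.89 (back) to 84/27 = 3.11 (leaning forward). The largest gap is 6/27 = 0.22 of a position, about 2 minutes against 40. With 35 subjects, 7 per row, the gap is zero.

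**What it does not do.** In a cyclic five-row square each posture follows the same predecessor in 4 of its 5 rows, so carry-over stays tied to posture.

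**The case against.** Four points can be made for the plan as written.

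First, the protocol never says that the order is fixed. A reader might infer that all subjects do the maneuvers in the same order. That is the natural reading of a numbered list, but it is not written, and the recorded start and end times will show what was done. This stands, and it makes the conclusion conditional. It does not remove the gap, because an order left open gives no assurance of balance.

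Second, a reader might go on to say that posture is fully confounded with wear time and that no analysis could separate them. The documents do not support that. Wear runs to 12 to 16 hours, quiet sitting is recorded at three points, and continuous recordings exist within each window. Two models in the table above are estimable. What remains is that each needs an assumption and that neither is planned in Section 7.

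Third, the objective is only to observe variation, with no endpoint or test, and summaries by maneuver and across time can both be produced. This is right: it would be wrong to say the objective goes unanswered. But a descriptive posture difference is no easier to interpret for being descriptive.

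Fourth, the stabilisation period, the initial sitting and the settling before each timed start already remove some early drift and carry-over. They reduce the problem by an unknown amount and do not break the link between posture and position.

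**Conclusion.** The point holds in a limited and conditional form. The order of the five maneuvers is neither specified nor counterbalanced. If the listed order is used for all subjects, posture differences within that roughly 50-minute block cannot be separated from order or elapsed time without modelling assumptions that Section 7 does not plan. This weakens the descriptive maneuver comparison under Objective 3.2.

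No size in milliseconds should be attached. Under linear drift, the contrast between standing and leaning forward would carry 40/60, or two thirds, of the hourly drift, but the documents give no drift rate. The pilot standard deviation of 8.36 in Section 9.1 describes differences between the two devices, so it is not a yardstick for a contrast between WCD postures.

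The EMAT equivalence test uses quiet sitting only and is untouched. This is a cheap improvement, not a defect that threatens the study's conclusion.

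**What to change.** In Section 5.5, keep quiet sitting first. Assign the order of 5.5.1 to 5.5.5 from a five-row Latin square keyed to the sequential identification number given at enrollment (Section 5.3). That gives 5 or 6 subjects per row at n = 27 and 7 per row at n = 35. If first-order carry-over is also to be balanced, use a ten-sequence Williams design instead, with 2 or 3 subjects per sequence at n = 27 and 3 or 4 at n = 35. Record the assigned sequence on the case report form. In Section 7, summarise each measure by posture and by position in the sequence.

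The cost is a printed order list and one form field, with no added procedure, staff or subject time. There are three downsides: the coordinator has to follow a subject-specific order, the change needs IRB approval before use (Section 13), and comparisons of the initial quiet sitting with the postures stay tied to order.

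If the order is not changed, the protocol should state which order is used and say in Section 7 that posture and sequence are not separated in the planned summaries.
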